**Table 4.1: Criteria for Permanently Discontinuing Study Drug for Elevations of Aminotransferase and/or Bilirubin**

Discontinuation Criteria	Confirmation Period
Serum AST or ALT > 3 x ULN and total bilirubin of > 2 x ULN	Repeat testing 3-7 days later to confirm laboratory results
AST or ALT > 5 x ULN	Repeat testing 3-7 days later to confirm laboratory results

#### **4.1.5. Withdrawal Procedures**

If a subject withdraws from the study, the Investigator or designee will complete and report the observations in the eCRF as thoroughly as possible up to the date of withdrawal including the date of last treatment and the reason for withdrawal.

If the subject is withdrawn due to an AE, the Investigator will follow the subject until the AE has resolved or stabilized.

The End of Study Treatment visit will be conducted within 21 days after administration of the last dose of study treatment (ie, the last dose of any study drug administered). At 40 days after the last dose a telephone call will be placed to the subject to record AEs.

For subjects with positive anti-patritumab neutralizing antibody in the serum sample drawn at the End of Study Treatment visit, additional serum samples should be obtained every 3 months for antibody measurement until the antibody level returns to baseline (or becomes negative) or up to 1 year from the last dose of study drug or if the subject starts another therapy for their cancer, whichever occurs first. A PK sample for patritumab will be collected at the time of HAHA collection for interpretation of HAHA results.

#### **4.1.6. Reasons for Discontinuation of Study Participation**

Subjects may terminate participation with study procedures if any of the following occurs:

- Subject withdraws consent to participate in study procedures
- Subject dies
- Study is terminated by sponsor
- Subject is lost to follow-up

Note: All subjects will be followed for survival status even after consent for study procedures is withdrawn. Subjects discontinued from the study because of withdrawal of consent will be followed for survival by collecting public records (eg, death certificates) unless prohibited by local laws.

**4.1.7. Subject Replacement**

Subjects will not be replaced in this study.

**4.1.8. Subject Re-screening Procedures**

Re-screening is permitted for any subject who failed to meet reversible or transient eligibility criteria upon initial screening. The subject identification number must remain the same at the time of re-screening. The initial reason why the subject is ineligible for the initial evaluation will be recorded on the Screening Log. No data from the initial evaluation will be entered into the clinical database for a subject who is re-screened.

## **5. TREATMENTS ADMINISTERED**

### **5.1. Investigational Products**

The Investigator must ensure that the blinded investigational product (ie, patritumab) will be used only in accordance with the protocol, as specified in Section 3.1.2. Placebo will be provided in a matching vial.

The vial labels will contain a description of the contents, batch number, and where appropriate, storage conditions and any additional statements as required by local regulations.

Daiichi Sankyo will provide carboplatin for this study. Wherever possible, commercial supplies of cetuximab and cisplatin will be supplied by the clinical site.

Daiichi Sankyo will only supply cetuximab and cisplatin to those sites that are not able to supply themselves.

#### **5.1.1. Method of Assigning Subjects to Treatments and Blinding**

Approximately 105 subjects who have an HRG expression value and HPV status (+/-) will be assigned randomly in a blinded manner by the Interactive Web/Voice Response System (IxRS) to the patritumab or the control arms in a 2:1 stratification (approximately 70 HRG-high and approximately 35 HRG-low subjects).

Please refer to Section 3.1 and Figure 3.1 for details.

#### **5.1.2. Method of Assessing Treatment Compliance**

All study drugs will be administered at the study site, under the supervision of the Investigator or designee in accordance with the protocol, to subjects participating in the clinical study. Administration of study drugs, including time of administration and dose administered, must be recorded in the eCRF.

#### **5.1.3. Labeling and Packaging**

The vial label will contain a description of the contents, batch number, and where appropriate, storage conditions and any additional statements as required by local regulations.

#### **5.1.4. Preparation**

Patritumab will be provided as a sterile lyophilisate with 240 mg/vial to be reconstituted with 8 mL water for injection to obtain a concentration of 30 mg/mL patritumab solution. Placebo lyophilisate will be diluted in an identical manner.

Subjects will be dosed based on the previous visit's weight. If the subject's weight at any visit has changed by  $\pm 10\%$  from the previous visit weight, the dose will be recalculated.

Patritumab or placebo will be prepared for each subject from allocated vials. Multiple individually numbered vials will be allocated to the subject via the IxRS and confirmed

on a subject/visit vial allocation report. Allocation of vials is not possible outside the IxRS. Concerns may be discussed with the CRO or Sponsor.

Refer to the Pharmacy Manual for detailed information regarding the preparation and administration of patritumab or placebo. Cetuximab, cisplatin, and carboplatin will be prepared according to the package insert.

#### **5.1.5. Storage**

Acknowledgement of drug shipments is managed through the IxRS to ensure materials are received in good condition before use. Drug supplies must be stored in a secure, limited access storage area under the recommended storage conditions.

Patritumab or matching placebo powder must be stored in a refrigerator set between 2°C and 8°C, and protected from light. Exposure to temperatures outside the recommended range or vigorous shaking of reconstituted drug product solution should be avoided. Temperature excursions outside the recommended range should be reported to the CRO and Sponsor. Once thawed, the product solution should not be refrozen.

Storage conditions for cetuximab, cisplatin, and carboplatin will follow respective labeling.

Records of the actual storage conditions during the period of the study must be maintained (eg, records of the date and time and the initials of the person checking, the “working day” temperatures of the refrigerator used for storage of trial supplies, continuous temperature recordings or regularly maintained temperature alarm systems used in conjunction with temperature recording).

#### **5.1.6. Drug Accountability**

When a drug shipment is received, the Investigator or designee will check the amount and condition of the drug, check for appropriate local language in the label, and drug expiration date. The original shipment document will be retained at the site.

A Drug Accountability Record (separate from the eCRF) will be provided for patritumab/placebo, cetuximab, cisplatin, and/or carboplatin if applicable. The record must be kept current and should contain the dates and quantities of drugs received, the subject’s details (ie, identification number and/or initials or supply number, as applicable), for whom the drug was dispensed, the date and quantity of drug dispensed, as well as the initials of the dispenser.

At the end of the study, or as directed, the unused patritumab/placebo and carboplatin, if applicable, in addition to cetuximab and cisplatin supplies, if provided by the sponsor, will be returned to a designee as instructed by the Sponsor. The drug supplies will be returned only after the study monitor has completed a final inventory to verify the quantity to be returned and reconciled any discrepancies. The return of the drug supplies must be documented and the documentation included in the shipment. At the end of the study, a final Investigational Product reconciliation statement must be completed by the Investigator or designee and provided to the Sponsor. Unused drug supplies may only be sent for destruction by the pharmacy, per sites’ standard operating procedures (SOPs) if the sites have been given permission from the sponsor in writing following SOP review.

If permission has not been given to destroy unused drug supplies locally they must be returned as instructed.

All investigational product inventory forms must be made available for inspection by a Sponsor's authorized representative or designee and regulatory agency inspectors. The Investigator or designee is responsible for the accountability of all used and unused study supplies at the site.

#### **5.1.7. Guidelines For Dose Modifications**

For those subjects who continue treatment, the Investigator will evaluate which hematological and/or non-hematological toxicities are attributed to which drug(s), and adjust the dose of one or more of the drugs as recommended below.

If a subject experiences an unacceptable toxicity to cisplatin, the Investigator will be able to withhold drug, reduce dose, or switch to carboplatin. If the Investigator chooses to start treatment with carboplatin, then carboplatin will be administered throughout the study. If a subject also experiences an unacceptable toxicity to carboplatin, then carboplatin treatment will be withheld or dose reduced.

Subjects with unacceptable toxic effects of one of the study drugs will receive only the tolerated drugs until disease progression.

- If patritumab/placebo needs to be discontinued, the subject will be withdrawn from the study
- In subjects whose cisplatin or carboplatin therapy is discontinued, reduced, or delayed, the patritumab and cetuximab will be continued and subjects will continue to undergo tumor assessments at 6 week intervals until disease progression or unacceptable toxicity
- In subjects whose cetuximab dose is discontinued, reduced, or delayed, the patritumab will be continued. Cisplatin or carboplatin will be administered for a maximum of 6 cycles
- In subjects whose cetuximab and cisplatin or carboplatin are either discontinued or delayed, patritumab will be continued as monotherapy

In addition to the recommendations provided below, please refer to the respective current prescribing information for detailed recommendations on managing suspected toxicities, for guidance on withholding, dose reductions, and discontinuation. If toxicities occur, it is up to the discretion of the Investigator to dose reduce or withhold one or more medications until recovery or resolution of the AE to Grade 0 or 1.

In individual cases, if a subject discontinues study drugs for an extended time period, the subject may restart study drugs at the discretion of the investigator after discussion with the Sponsor and CRO's medical monitors.

Investigators may contact the Sponsor's medical monitor to discuss any question regarding dose modification or discontinuation of study drugs.

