#### **4.1.3. Removal of Subjects From Therapy**

Any subject may withdraw from the study treatment or from the study at any time without specifying a reason. If a subject withdraws from the study treatment or study, the reason for withdrawal will be recorded on the eCRF. The Investigator will complete and report the observations as thoroughly as possible up to the date of withdrawal including the date of last treatment and the reason for withdrawal.

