#### **4.1.4. Reasons for Discontinuation of Study Treatment**

Reasons for discontinuation of a subject from the study include: PD as per RECIST 1.1 or clinician's assessment, AE, death, withdrawal of consent by subject, significant protocol violation, or sponsor decision to terminate the study.

In the event of a decision to discontinue study drug treatment the investigator will contact the subject directly to explain the circumstances requiring study treatment to be stopped. The subject will be instructed to attend the safety follow-up visit required by the study protocol, and the treating physician will discuss alternative treatment options with the subject.

The reason for discontinuation will be recorded.

Subjects may be withdrawn from the study after signing informed consent for the following reasons:

- Adverse Event
- Lost to Follow-up
- Withdrawal of Consent by Subject
- Physician Decision
- Death
- Pregnancy
- Progressive Disease

- Study Terminated by Sponsor
- Other

All subjects who are withdrawn from the study should complete protocol specified withdrawal procedures, unless they withdraw their consent (Section 4.1.5).

Elevations in AST/ALT and/or total bilirubin that meet the criteria described in Table 4.1 require permanent discontinuation of the subject from patritumab/placebo and cetuximab.

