**Table 5.2: Dose Delays/Reductions for Toxicities Related to Patritumab**

Grade	Action
1	Continue current dose level
2	Continue current dose level
3	Discontinue patritumab/placebo for up to 3 weeks until the event has recovered to Grade 1 or baseline. a Administer patritumab at a dose that is decreased by one dose level for subsequent cycles. A maximum of 1 dose reduction from the 9 mg/kg IV maintenance dose to 6 mg/kg IV maintenance dose will be permitted. No dose reductions below patritumab 6 mg/kg will be allowed.
4	Discontinue patritumab/placebo for up to 3 weeks until the event recovers to Grade 1 or baseline. a Discuss the event with the sponsor's Medical Monitor or designee before restarting patritumab/placebo. If the investigator and the sponsor's Medical Monitor/designee agree, the weekly maintenance dose will also be decreased from 9 mg/kg IV to 6 mg/kg IV.

a If the subject fails to recover to Grade 1 or baseline and dose must be delayed >3 weeks, the subject will be withdrawn from all study treatment, but should continue to undergo all follow-up evaluations

To receive patritumab, a subject's ANC must be  $\geq 1.5 \times 10^9/L$  ( $\geq 1500/mm^3$ ) and platelet count must be  $\geq 100 \times 10^9/L$  ( $\geq 100,000/mm^3$ ). Patritumab may be withheld for up to 3 weeks to allow cell counts to recover to these values. Dose administration may be delayed no more than 3 weeks to allow for recovery. If the dose is delayed more than 3 weeks, the subject will be withdrawn from study treatment, unless discussed and agreed with the sponsor.

All subjects should be carefully monitored for possible infusion reactions during the administration of patritumab/placebo. If, during infusion, a subject experiences mild to moderate symptoms suggestive of infusion reaction (such as fever and chills, with or without nausea/vomiting, pain, headache, dizziness, dyspnea, hypotension), slow down the infusion up to 120 minutes (see Section 3.1.2.1 for administration of patritumab/placebo). All subsequent infusions should be administered at the same slow rate (up to 120 minutes).

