**Table 5.5: Cisplatin Dose Modifications and Discontinuations\* for Toxicities**

Toxicity	Dose Modification/Discontinuation
Hematological	A repeat course should not be given until circulating blood elements are at an acceptable level (ie, platelets $\geq 100 \times 10^9/L$ , white blood cells $\geq 4 \times 10^9/L$ )
Febrile neutropenia/infection	The first episode of febrile neutropenia or infection will result in reduction by 20% of cisplatin dose. If there is a second episode, despite dose reduction, the subject must receive prophylactic antibiotics during subsequent cycles. If there is a third episode, the subject will be withdrawn from study.
Neutropenia	Grade 2 or 3: cisplatin treatment delay until < Grade 1. Grade 4: cisplatin treatment delay until < Grade 1; dose reduction of all further doses of cisplatin by 20%.
Nephrotoxicity	A repeat course of cisplatin should not be given until the serum creatinine is below 1.5 mg/100 mL, and/or the urea is below 25 mg/100 mL
Thrombocytopenia	Grade 1: cisplatin treatment delay until platelets $\geq 100,000/mm^3$ . $\geq$ Grade 2: cisplatin treatment delay until platelets $>100,000/mm^3$ , dose reduction of all further doses of cisplatin by 20%

Toxicity	Dose Modification/Discontinuation
Organ Toxicity	Grade 2: Delay chemotherapy until $\leq$ Grade 1. $\geq$ Grade 3 or more: Delay chemotherapy until $\leq$ Grade 1; dose reduction of all further doses of cisplatin by 20%. Do not delay or reduce cisplatin dose if there are asymptomatic increases in transaminases, cetuximab-induced skin reactions, and subclinical side effects (e.g. nausea, vomiting, alopecia, altered taste).
Ototoxicity	Criteria for hearing testing
Neuropathy	In case of sensory neuropathy $\geq$ Grade 2, change cisplatin to carboplatin

Note: Please refer to the cisplatin package insert for additional information on potential toxicities and their management. When cisplatin is administered in combination with other agents such as cetuximab, refer to their respective product information. \*If events do not recover within 3 weeks, discontinue cisplatin treatment.

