When an emergency unblinding has occurred, an automatic notification (via e-mail) will be sent to the investigator and selected Daiichi Sankyo study personnel from the IxRS vendor. The notification will not contain any unblinding information. This will trigger the follow up process to document the unblinding by completing the Emergency Unblinding by Investigator Form (to be provided to the CRO medical monitor by study personnel upon receipt of IxRS notification) and submission to Daiichi Sankyo Clinical Safety and Pharmacovigilance; please refer to the form for completion instructions.

Once the study treatment has been unblinded for a specific subject, the study treatment should be discontinued for the subject, and the subject should leave the study treatment phase. The end of treatment and follow-up assessments for the subjects will be performed as defined in the protocol.

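### Protocol 5.1.7 and Table 5.5 withdraw subjects from the study where study treatment is probably meant; a site following the words literally could end PFS scans early

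*Protocol*

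**What the plan says.** Two dose-modification rules remove a subject from the study:

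- Protocol 5.1.7, first bullet: "If patritumab/placebo needs to be discontinued, the subject will be withdrawn from the study".
- Protocol Table 5.5, febrile neutropenia/infection row: "If there is a third episode, the subject will be withdrawn from study".

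Section 4.1.4 is headed as dealing with study treatment, yet opens "Reasons for discontinuation of a subject from the study include: PD as per RECIST 1.1". It later lists adverse event and progressive disease among reasons for withdrawal from the study.

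Elsewhere the protocol separates the two ideas. Section 4.1.3 says: "Any subject may withdraw from the study treatment or from the study at any time without specifying a reason". For a patritumab delay beyond 3 weeks, the text after Table 5.2 says "the subject will be withdrawn from study treatment, unless discussed and agreed with the sponsor", and footnote a of that table says "the subject will be withdrawn from all study treatment, but should continue to undergo all follow-up evaluations". After emergency unblinding (5.1.9), "the study treatment should be discontinued for the subject, and the subject should leave the study treatment phase".

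Protocol 6.2.11, Protocol 7 and SAP 5.1 keep tumour assessments going in subjects who are off treatment. They end at progression, death, new anticancer therapy, withdrawal of consent, loss to follow-up or study closure.

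**The concern.** The primary endpoint is investigator-assessed radiographic PFS, so it depends on scans continuing after a toxicity stop. A literal path to ending them exists. Section 5.1.7 withdraws the subject from the study. Section 4.1.4 sends withdrawn subjects to the procedures in 4.1.5. That section lists an end-of-treatment visit and then "At 40 days after the last dose a telephone call will be placed to the subject to record AEs", with no mention of further scans. A site could take 6.2.11 as not applying, because it is addressed to subjects discontinued from study treatment.

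If scans stop, censoring rule 1 in SAP 5.1.1 censors PFS at the last evaluable post-baseline scan. Rule 3 censors even a death if it falls more than 13 weeks after that scan. The PFS sensitivity analyses in SAP 8.2.4.1 (clinical progression as an event, and a changed HRG cutoff) do not test this. Scans not done cannot be recovered later.

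**Working it through.** **Text comparison**

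| Situation | Place | Subject leaves | Follow-up or scans |
|---|---|---|---|
| Patritumab/placebo must stop | 5.1.7, first bullet | the study | not stated |
| Third neutropenia/infection episode | Table 5.5 | the study | not stated |
| Patritumab delayed over 3 weeks, toxicity unrecovered | Table 5.2, footnote a | all study treatment | continue |
| Treatment stopped without imaging progression | 6.2.11 | study treatment | continue |
| Any treatment stop | Protocol 7; SAP 5.1 | treatment | continue |
| Reasons to end study procedures | 4.1.6 | study procedures | drug stop not listed |

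The third row is one of the situations covered by the first, with the opposite consequence. Section 4.1.6 conflicts only by omission. Other mandatory stops (liver criteria in Table 4.1, severe infusion reactions in 5.1.7.1, interstitial lung disease in 9.3.2) do not say that tumour assessments continue.

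There are two further clashes over drugs. The sentence introducing the 5.1.7 bullets keeps subjects on whichever drugs they tolerate until progression. The second bullet continues patritumab and cetuximab when platinum is stopped, whereas Table 5.5, the cisplatin table, removes the subject altogether.

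**Design figures (Protocol 11.10)**

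Inputs: HR 0.56, one-sided alpha 0.10, 80% power, 1:1 allocation. Schoenfeld events = 4(1.2816 + 0.8416)² / (ln 0.56)² = 53.6, against the stated 53. Power with 53 events = Φ(√53/2 × 0.580 − 1.2816) = 0.796. The correction changes neither figure.

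**Room in the event count**

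The trigger needs 53 of 70 HRG-high subjects (75.7%). Take control hazard ln 2/4.2 = 0.1650 and patritumab hazard ln 2/7.5 = 0.0924 per month. Read the 10% dropout as per 12 months (an assumption), so η = −ln 0.9/12 = 0.00878. With 12 months' accrual and 10 months' follow-up, and h = λ + η, expected events per arm are 35 × (λ/h) × [1 − (e^(−10h) − e^(−22h))/(12h)]:

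- Control: 35 × 0.9495 × (1 − 0.0738) = 30.8
- Patritumab: 35 × 0.9132 × (1 − 0.2105) = 25.2
- Total at month 22: 56.0, which is 3.0 above the trigger

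This treats progression as seen at once; recording it at scheduled scans lowers the total. At month 22 events arrive at 35 × (0.1650 × 0.0738 + 0.0924 × 0.2105) = 1.11 per month. One lost event therefore costs about 1/1.11 = 0.9 month there, and less if the 53rd event falls earlier.

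**Loss per literal stop (illustration)**

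A literal stop loses at most one event. A simulation under the design medians and scan schedule gives 0.54–0.66 of an expected event by month 22 if no stopper starts new therapy. It gives 0.28–0.37 if half do so 1.5 months after stopping, since rule 2 censors those subjects anyway. Assumptions not in the documents: stops spread over months 0.3–5, stoppers at 1 or 2 times the design hazard, 20% of PFS events being deaths without progression, and median survival of 6 months after progression. The scan due at the end-of-treatment visit is included. Five literal stops, for example, would lose 5 × 0.28 = 1.4 to 5 × 0.66 = 3.3 events.

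**Bias**

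In the same model, I took nominal stop rates from 5% in each arm to 10% control and 20% patritumab, with every stop handled literally. The HR moved by −0.013 to +0.008. The larger shift is about 0.013/0.56 = 0.023 on the log scale, against a standard error of 2/√53 = 0.27.

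**The case against.** The harmless reading has strong support. The two rules are dose-modification text and never say that scans end; that is inferred from the silence of 4.1.5. Protocol 6.2.11, Protocol 7 and SAP 5.1 are explicit on scans and agree. Section 4.1.4 uses the same phrase for progressive disease. Taken literally there, every progressor would leave the study, which makes no sense beside the survival follow-up in 6.3. Section 5.1.7 also invites contact with the medical monitor on discontinuation questions. Many sites would keep scanning.

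This stands as an argument that the wording is a slip and that the harm is only possible. It does not remove the conflict. The rules are mandatory, Section 4.1.3 gives withdrawal from the study its own meaning, and nothing reconciles the two sets of passages.

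A reader might infer that the plan orders PFS follow-up to end at toxicity. The scan-governing sections say otherwise. A reader might also infer a loss of power. Protocol 11.2 triggers the analysis at no fewer than 53 HRG-high events, so lost events mean delay. Nor should the chance of falling short of 53 events at month 22 be charged to this wording: that chance is already substantial with correct handling, and month 22 is approximate and does not cap the analysis.

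**Conclusion.** The conflict is certain; its effect is not. It is a minor internal inconsistency, wrong as written. The documents give neither the rate of patritumab/placebo stops before progression nor the share of sites that would act literally, so the number of lost events cannot be fixed. The likely cost is at most a few avoidable lost PFS events and some delay to the 53rd. That rests on few stops being handled literally and on the assumptions stated above.

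A reader might expect unequal toxicity stops to favour one arm. The documents do not support a direction: stop rates by arm and the prognosis of stoppers are not given, and the illustrative shift is small and takes either sign. OS is largely protected, because 4.1.6 and 6.3 keep survival follow-up going.

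**What to change.** Make three corrections in a protocol amendment, or in a site clarification letter pending one:

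1. **Section 5.1.7, first bullet.** Replace withdrawal from the study with discontinuation of patritumab/placebo. State once whether cetuximab and platinum also stop, and reconcile this with the introductory sentence on tolerated drugs. Add that tumour assessments continue per 6.2.11 and Section 7, and survival follow-up per 6.3.
2. **Table 5.5.** Say which drugs stop after the third episode: cisplatin only, which fits the second bullet of 5.1.7, or all study treatment. Add the same follow-up sentence.
3. **Section 4.1.4.** Refer to study treatment wherever treatment discontinuation is meant.

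The cost is drafting and notifying sites. No visits or scans are added beyond those already required, and the sample size and event target are unchanged.
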